#### 7.1.7 Excluded Treatments, Medical Devices, and/or Procedures During Study Period

The following treatments and/or procedures are excluded during the treatment period of the study (until SFU):

- any antitumor therapy other than AMG 420, such as:
  - cytotoxic and/or cytostatic drugs
  - radiation therapy (with the exception of radiotherapy for palliative care such as bone pain; this is only permitted after discussion with Amgen medical monitor)
  - immunotherapy

- any other immunosuppressive therapies (except for the management of acute, treatment-related toxicities such as transient - ie, for up to 2 weeks - use of corticosteroids and tocilizumab)
  - high-dose corticosteroid therapy (dexamethasone > 24 mg/day or equivalent) is only allowed for up to 7 days
- any other investigational agent
- treatment with medications known to cause QTc interval prolongation unless approved by the Amgen medical team (see [Section 12.10](#))
- any major surgery, except for surgery for palliative repair of pathologic fractures, as long as determined not to be due to disease progression
- none of the medications mentioned in [Section 7.8.2](#) are excluded during the study

#### **7.1.8 Vaccines**

**The use of vaccines except live and live-attenuated vaccines will be allowed during therapy per regional and institutional standard of care. Throughout the trial, SARS-COV-2 vaccination should be avoided within 3 days after the administration of AMG 420. In the event where a patient requires steroids for treatment of AEs, vaccination should be avoided while on steroids.**

#### **7.2 Method of Treatment Assignment**

An Amgen representative will notify the site(s) in writing when a cohort or study part, respectively, are open to screen and enroll subjects.

Subjects who meet eligibility criteria will be assigned to treatment with AMG 420.

The treatment assignment date is to be documented in the subject's medical record and on the enrollment eCRF.

#### **7.3 Blinding**

This is an open-label study; blinding procedures are not applicable.

#### **7.4 Dose Modification**

##### **7.4.1 Dose-cohort Study Escalation/De-escalation and Stopping Rules**

The DLT evaluation period (ie, DLT-evaluable period) will be the 4 weeks on AMG 420 treatment within the first treatment cycle, starting on day 1 (start of infusion). The DLT evaluation period may also be extended to assess events starting within the window in case the DLT definition is time dependent.

Treatment in AMG 420 cycle 1 will be considered complete and the subject will be DLT evaluable if the subject has completed the DLT evaluation period or experienced a DLT any time during the DLT evaluation period. A subject will be non-DLT evaluable if he/she drops out before completion of the DLT-evaluable period for reasons other than a

DLT. All available safety data for subjects who are non-DLT-evaluable will still be evaluated and considered in DLRT decisions (see also [Section 10.4.1.1.1.1](#)).

See [Section 5.2.1](#) for description of replacement of subjects.

A DLT will be defined as any of the events described below occurring in a subject during the DLT evaluation period unless clearly attributable to causes other than treatment with AMG 420. The CTCAE version 5.0 (see [Section 12.4](#)) will be used to assess toxicities/adverse events with the exception of CRS and TLS (see [Section 7.4.2.1.2.5](#) and [Section 12.12](#) for grading criteria of CRS and TLS, respectively).

- Death not clearly due to the underlying disease or extraneous causes.

Non-hematologic DLTs:

- Non-hematological adverse event grade 3 or higher, EXCEPT:
  - infection responding to antibiotic/anti-infective treatment within 48 hours
  - grade 3 fatigue or asthenia
  - grade 3 headache resolving to  $\leq$  grade 2 within 72 hours
  - grade 3 insomnia resolving to  $\leq$  grade 2 within 7 days
  - grade 3 fever resolving to  $\leq$  grade 2 within 72 hours
  - grade 3 nausea, vomiting, or diarrhea responding if successfully managed with optimal medical support and resolved within 72 hours
  - laboratory parameters of grade  $\geq$  3, not considered clinically relevant, and improved to grade  $\leq$  2 within 72 hours
- Any subject meeting the criteria for Hy's Law case (ie, severe drug-induced liver injury [DILI]) will be considered a DLT. A Hy's Law case is defined as: AST or ALT values of  $\geq 3 \times$  ULN AND with serum TBIL level of  $> 2 \times$  ULN or international normalized ratio (INR)  $> 1.5$  without signs of cholestasis and with no other clear alternative reason to explain the observed liver-related laboratory abnormalities (see [Section 7.4.3](#) for hepatotoxicity management and [Section 12.7](#) for further explanation of Hy's law case and management of hepatic function).

Hematologic DLTs:

- febrile neutropenia grade 4
- febrile neutropenia grade 3 unless responding to antibiotic/anti-infective treatment within 48 hours
- grade 4 neutropenia lasting more than 5 days, grade 4 thrombocytopenia lasting more than 7 days, grade 3 thrombocytopenia with hemorrhage or required platelet transfusion, or grade 4 anemia in the absence of detectable multiple myeloma as it may reflect a marrow toxic effect of AMG 420

The dosing schedule is described in the Schedule of Activities ([Section 2.2](#)).

---

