#### **7.8.2.1 Supportive Care**

Subjects should receive supportive care according to local guidelines for blood product support, antibiotics, antivirals, analgesics, etc

Please refer to [Section 7.4.2.1.2.2](#) and [Section 7.4.2.1.2.5](#) for management of CRS and infusion related reaction.

Oxygen administration as supportive measure is permitted during study treatment.

To prevent TLS, all subjects should receive at the discretion of the investigator appropriate hydration and supportive measures (eg, rasburicase) according to local standard of care and institutional guidelines. Please refer to [Section 7.8.2.7](#) for management guidelines of TLS.

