#### **7.8.2.5 Growth Factors**

The use of growth factors such as erythropoiesis-stimulating proteins as well as granulocyte colony stimulating factor (G-CSF) will be allowed during therapy per regional and investigator standard of care. However, growth factors are not allowed at inclusion (within 7 days of applicable screening assessment) and should be avoided, if subject's condition allows, in the first treatment cycle for better assessment of safety parameters.

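### The DLT definition can count a transfused or bleeding grade 3 thrombocytopenia but not the same event at grade 4 lasting 7 days or less, and its infection exception has no grade limit

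*Protocol*

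**What the plan says.** Protocol Section 7.4.1 defines a DLT by a list of clauses. Three parts of the list matter here.

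- **Thrombocytopenia.** The listed events are "grade 4 thrombocytopenia lasting more than 7 days, grade 3 thrombocytopenia with hemorrhage or required platelet transfusion". The grade 4 limb has a duration test and nothing else. The grade 3 limb has hemorrhage or transfusion as its test and no duration.
- **Infection.** Non-hematologic DLTs start from "Non-hematological adverse event grade 3 or higher, EXCEPT", followed by exceptions. One exception is "infection responding to antibiotic/anti-infective treatment within 48 hours", with no grade stated. The symptom exceptions beside it each name grade 3; the headache one, for example, begins "grade 3 headache resolving to". The laboratory exception states that it covers grade 3 and above.
- **Febrile neutropenia.** The list has "febrile neutropenia grade 4" without any exemption, and then "febrile neutropenia grade 3 unless responding to antibiotic/anti-infective treatment within 48 hours".

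Transfusion is open to every subject: Section 7.8.2.1 says "Subjects should receive supportive care according to local guidelines for blood product support".

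SAP Section 5 adds no definition. It leaves the classification to the investigator under Protocol Section 7.4.1. DLTs are the first-listed primary endpoint (Protocol Section 4.1) and the event counted in the enrollment-hold rule (Table 5-1).

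**The concern.** A toxicity definition should not become less likely to capture an event as the event gets worse. The platelet clause has that defect when followed as written, and a transfusion may itself end the grade 4 period before the 7-day limit. The infection clause has a different defect: the section applies one response exemption with a grade limit in one place and without a limit in another.

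At stake is the DLT count, which has four uses:

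- It is a primary endpoint, reported on about 10 subjects per dose level.
- It is the only input to the automatic pause in Table 5-1.
- It affects the denominator. A subject whose event is not labelled a DLT and who drops out in cycle 1 is not DLT-evaluable and may be replaced (Sections 5.2.1 and 7.4.1).
- It affects management. A DLT is a ground for permanent discontinuation under conditions set out in Section 7.4.2.1.3, while Table 7-2 has separate guidance for related events that do not meet the DLT criteria. Both places depend on Section 7.4.1 being unambiguous.

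**Working it through.** **1. Literal classification under Section 7.4.1**

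| Event in the DLT period | DLT by its own clause? |
|---|---|
| Grade 3 thrombocytopenia with hemorrhage or required transfusion | Yes, at any duration |
| Grade 4 thrombocytopenia, 7 days or less, with hemorrhage or required transfusion | No |
| Grade 4 thrombocytopenia, more than 7 days | Yes |
| Grade 3 infection responding within 48 hours | No |
| Grade 4 infection responding within 48 hours | No |
| Grade 3 febrile neutropenia responding within 48 hours | No |
| Grade 4 febrile neutropenia, whatever the response | Yes |

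Rows 1 and 2 are an inversion. Rows 4 to 7 show two rules for the same exemption. Grade 3 cannot be read in the platelet clause as grade 3 or worse, because the same section says so explicitly where it means that.

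**2. The plan's own figures**

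- Section 10.1 gives 65% to 89% for seeing at least one event in 10 subjects at true rates of 10% to 20%. The formula 1 − (1 − p)^10 gives 65.1% and 89.3%, so the figure reproduces.
- Table 5-1 follows from Section 10.3: a Beta(1,1) prior, posterior Beta(1 + x, 1 + n − x) for x DLTs in n subjects, and posterior mass divided by width for each of the intervals 0–20%, 20–33% and 33–100%. Enrollment halts if the top interval is highest. The minimum x is 2 for n = 2 to 4, 3 for n = 5 to 6 and 4 for n = 7 to 8, which matches the table. At n = 1 the model would flag 1 of 1, while the table requires 2.

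**3. One uncounted event at each boundary**

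| DLTs / subjects | Under | Target | Over | Result |
|---|---|---|---|---|
| 2 / 4 | 0.29 | 1.13 | 1.19 | hold |
| 1 / 4 | 1.31 | 2.08 | 0.70 | continue |
| 3 / 6 | 0.17 | 1.04 | 1.24 | hold |
| 2 / 6 | 0.74 | 2.11 | 0.86 | continue |
| 4 / 8 | 0.10 | 0.93 | 1.28 | hold |
| 3 / 8 | 0.43 | 1.97 | 0.98 | continue |

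In a cohort of 10, one event also moves the reported rate by 1/10, or 10 percentage points.

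**4. Illustration only.** The documents do not give the share of DLT-like events that would fall in these gaps. Taking it as 10%, 25% or 50% purely as an assumption, and running Table 5-1 subject by subject with counted rate p × (1 − share), the probability that a hold is triggered by subject 8 is:

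| True rate p | All counted | 10% escape | 25% escape | 50% escape |
|---|---|---|---|---|
| 33% | 47% | 40% | 29% | 14% |
| 40% | 61% | 53% | 40% | 20% |
| 50% | 79% | 70% | 56% | 30% |

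**The case against.** The best case for leaving the text alone is that other provisions catch these events.

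- Appendix 12.4 asks for a separate record at each severity level. A grade 4 episode that falls to grade 3 could therefore have a grade 3 record linked to the transfusion and be counted.
- A hemorrhage of grade 3 or higher could count in its own right as a non-hematologic event, and deaths have their own clause.
- The primary endpoint also includes all treatment-emergent events. SAP 9.6.2 tabulates grade 3 or higher events and SAP 9.6.3 gives worst-grade shifts for platelets.
- The dose level review team sees all safety data before cohort 2 opens, and enrollment can be stopped at any time.
- The laboratory exception also extends above grade 3, so the exceptions are not uniformly limited.
- Amendment 5 reports that the program is terminated, so rewording may affect little further enrollment.

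Much of this stands. The events would remain visible in the safety tables, and the fatal ones would be counted unless clearly due to the disease or an extraneous cause. But per-grade coding, separate coding of a bleed and team review all rest on judgement. None of them says that the grade 4 event is a DLT, and none corrects the count in Table 5-1. The laboratory exception weakens the comparison with the symptom list, but it states its grade range and is confined to findings judged not clinically relevant. The conflict with the febrile neutropenia clauses is unaffected.

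A reader might go further in two ways that the text does not support. One is to call the infection clause an inversion as well. It is not, because grade 3 infections that respond are exempt on the same terms; what is missing is a grade limit. The other is to see a similar fault in grade 4 neutropenia, whose duration growth factors could shorten. No milder neutropenia without fever is a DLT, so there is no inconsistency across grades, and Section 7.8.2.5 already says that growth factors "should be avoided, if subject's condition allows, in the first treatment cycle for better assessment of safety parameters".

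**Conclusion.** The point holds in two parts. The platelet clause is the stronger: followed literally, grade 4 thrombocytopenia with hemorrhage or transfusion, lasting 7 days or less, is not a DLT while the grade 3 event is. The infection exception conflicts with the grade 3 limit that the same section puts on the same 48-hour exemption for febrile neutropenia.

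The consequence of one uncounted event is exact: a hold becomes continued enrollment at 2/4, 3/6 and 4/8, and is otherwise unchanged unless the count sits at such a boundary. The frequency is unknown. A reader might infer a large undercount from the 65.7% of first-in-human subjects with infections (Section 3.2.2.4), but that figure covers every grade and cycle, and the infection summary there gives no rate for grade 4, responding, cycle 1 infections. It gives no rate for thrombocytopenia either. The hold probabilities above therefore show sensitivity to an assumed share and do not forecast the loss.

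This is a defect of definition worth correcting. It does not show that the DLT rate will in fact be understated by a given amount.

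**What to change.** In Protocol Section 7.4.1, reconcile the grade 3 and grade 4 thrombocytopenia limbs with each other, and the infection exception with the febrile neutropenia clauses, so that for the same circumstances DLT status cannot fall as grade rises. The sponsor should choose the thresholds, because DLT status also bears on discontinuation under Section 7.4.2.1.3. The text should also say how an episode recorded at more than one grade is classified.

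Have the DLT analysis in SAP 9.6.2 refer to the reconciled definition. Even if little enrollment remains, this settles how the recorded events are counted.

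The cost is a few wording changes. Event grades, onset and resolution dates, and concomitant treatments are already recorded. The downside is that the reported DLT rate may be slightly higher.

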## **7.4.2 Dosage Adjustments, Delays, Rules for Withholding or Restarting, Permanent Discontinuation**

### **7.4.2.1 Amgen Investigational Product: AMG 420**

The reason for dose change of AMG 420 is to be recorded on each subject's eCRF(s).

#### **7.4.2.1.1 Infusion Interruptions and Re-Start in Case of Technical/Logistical Issues**

The administration of AMG 420 should not be interrupted, if possible. In case of infusion interruption due to any technical or logistical reason (eg, a technical problem with the infusion pump, diagnostic measurements, or the investigational product is incorrectly prepared or administered), the interruption should be as short as possible, and the infusion continued at the earliest time possible.

If the interruption is longer than 4 hours, re-start of the infusion should be performed in the hospital, under the supervision of the investigator. If the interruption occurs during cycles 1 or 2, the subject should be observed for 24 hours after re-start for possible side effects. If the interruption occurs in cycle 3 or beyond, the subject should be observed for 4 hours. Premedication as described in [Section 7.1.4](#) must be administered prior to resumption of AMG 420 infusion, if applicable.

The assessments that should be performed prior to re-start of infusion as for cycle 1 days 1 and 2 are specified in the Schedule of Activities (see [Section 2.2](#)).

Every interruption longer than 1 hour should be documented on the eCRF.

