#### **7.1.1.4 Dosing Instructions**

The Amgen investigational product (AMG 420) will be dispensed at the research facility by a qualified staff member.

At the beginning of a treatment cycle a physician or nurse trained in emergency medical care must be available when the infusion of investigational product (AMG 420) is started for immediate intervention in case of complications.

AMG 420 will be delivered using infusion pumps approved for use by the appropriate regulatory authority for the country in which the subject is undergoing treatment.

AMG 420 solution for infusion will be prepared in bags for IV infusion and delivered through infusion lines.

The drug will be administered as a cIV infusion at a constant flow rate.

The drug should not be administered as a bolus and flushing residual drug at the time of bag change is prohibited. The final solution for infusion should be administered through a sterile 0.2 µm in-line filter.

Infusion bags should be changed in accordance with country regulations and local pharmacy standards for infusion of compounded sterile products up to 48 hours in the US and up to 96 hours in Australia and Europe.

The start time of infusion should be chosen carefully to avoid any interference or inconvenience with time points of safety assessments, PK/pharmacodynamic measurements, and infusion bag changes.

Any infusion interruption that is longer than 1 hour should be recorded on the eCRF (including start date/time and stop date/time) with the exception of adverse events. Any infusion interruption due to an adverse event, independent of the duration of the interruption, should be recorded on the eCRF.

Details for handling infusion interruptions are outlined in [Section 7.4.2](#).

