#### **7.1.1.4.1 AMG 420 Inpatient Dosing/Hospitalization**

Minimum hospitalization times for subjects will be as follows:

- Cycle 1: 48 hours or 6 days after start of infusion if step dosing is utilized.
- Cycle 2: 24 hours monitoring after start of infusion; longer monitoring can be decided upon at investigator's discretion.
- Cycles 3 and 4: 4 hours monitoring after start of infusion.
- Cycle 5 and subsequent cycles: hospitalization not required unless subject experiences an adverse event requiring hospitalization as indicated in [Section 2.2](#) of the study protocol or if clinically indicated. The length of hospitalization required in these cases is to be determined by the investigator.
- Re-start of treatment after an interruption due to adverse event: 48 hours.
- Re-start of treatment after an interruption of > 4 hours due to technical/logistical issue: 24 hours.
- Any cycle with dose re-escalation: 48 hours after dose re-escalation.

For cycles 1 and 2 in-hospital administration, study sites must have immediate access to a medical intensive care unit staffed by critical care providers. Prior to hospital discharge, vital signs will be measured in order to detect possible signs and symptoms of infusion reactions or CRS. If required for logistical reasons (eg, long travel times),

subjects may be hospitalized the day before start of dosing (day -1) of any cycle, as well as at the end of infusion (EOI) for cycle 1 for required PK samples.

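### From cycle 3 on, the protocol gives two different in-hospital times, 24 hours and 4 hours, for the same re-start after a technical interruption of more than 4 hours

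*Protocol*

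**What the plan says.** Three places in the current protocol text cover a re-start after a technical or logistical interruption of more than 4 hours.

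- **Section 7.1.1.4.1 (inpatient dosing).** The list opens with "Minimum hospitalization times for subjects will be as follows" and includes the item "Re-start of treatment after an interruption of > 4 hours due to technical/logistical issue: 24 hours". The item does not mention the cycle.
- **Synopsis, inpatient dosing.** The same list is repeated, with the same item and no limit by cycle.
- **Section 7.4.2.1.1 (technical/logistical interruptions).** The trigger and setting are the same: "If the interruption is longer than 4 hours, re-start of the infusion should be performed in the hospital, under the supervision of the investigator". The section then splits by cycle. For the early cycles: "If the interruption occurs during cycles 1 or 2, the subject should be observed for 24 hours after re-start for possible side effects". For later cycles: "If the interruption occurs in cycle 3 or beyond, the subject should be observed for 4 hours".

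The cross-references do not settle the matter. The footnotes to the schedules of activities (Tables 2-1, 2-2 and 12-4) send the reader to Section 7.1.1.4.1 for hospitalization requirements. Section 7.1.1.4 says "Details for handling infusion interruptions are outlined in" Section 7.4.2, and Section 7.1.1.4.2 sends outpatient interruptions and re-starts to Section 7.4.2 as well.

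**The concern.** A site handling a pump failure of more than 4 hours in cycle 3 or later finds 24 hours if it looks up hospitalization and 4 hours if it looks up interruptions. Two sites acting in good faith could therefore monitor the same event for different lengths of time. A site that follows the shorter figure would also be out of line with a stated minimum elsewhere in the same protocol.

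The stake is a safety-monitoring rule that cannot be applied or audited consistently, together with deviations that arise only from the wording. The situation is a realistic one. AMG 420 is given as a continuous infusion that may run in the outpatient setting, and Section 7.4.2.1.1 itself names pump problems as a cause of interruption. The protocol plans about 15 sites for about 20 subjects, so each site will see few such events and will have to rely on the text.

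**Working it through.** No sample size, power or event count enters here. The check is a comparison of the texts, plus two small pieces of arithmetic on size.

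**Step 1: is it the same event?** Section 7.1.1.4.1 and the synopsis specify a technical or logistical cause, an interruption of more than 4 hours, and a re-start. Section 7.4.2.1.1 specifies the same cause, the same threshold, and a re-start in hospital under the investigator's supervision. The triggers match.

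**Step 2: compare by cycle.**

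| Cycle in which the interruption occurs | Section 7.1.1.4.1 and synopsis | Section 7.4.2.1.1 | Agreement |
|---|---|---|---|
| 1 or 2 | 24 h minimum | 24 h | yes |
| 3 or later | 24 h minimum (no limit by cycle) | 4 h | no |

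From cycle 3 on the difference is 24 − 4 = 20 hours, and the ratio is 24 / 4 = 6.

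**Step 3: can a site comply with both?** Yes, by keeping the subject 24 hours, because the list sets a minimum stay and an observation of 4 hours falls within it. The reverse fails: release at 4 hours under Section 7.4.2.1.1 falls 20 hours short of the listed minimum.

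**Step 4: is there a rule of precedence?** None was found. The schedule footnotes lead to the 24-hour figure; Sections 7.1.1.4 and 7.1.1.4.2 lead to the section with the 4-hour figure. The parallel rule for re-start after an adverse event is aligned: Section 7.4.2.1.2.3 gives at least 48 hours and cites Section 7.1.1.4.1, which also gives 48 hours. The technical rule has no such link.

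**Step 5: how much of treatment falls where the texts differ?** Inputs are the expected median treatment period of about 8 months (Section 5.3.2), a 6-week cycle of 42 days (Section 7.1.1.2), and 30.4 days per month (the SAP's convention).

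- Treatment time: 8 × 30.4 = 243.2 days.
- Cycles: 243.2 / 42 = 5.8.
- Time in cycles 1 and 2: 2 × 42 = 84 days.
- Share in cycle 3 or later: (243.2 − 84) / 243.2 = 159.2 / 243.2 = about 65%.

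This applies to a subject treated for the expected median time, with no cycle delays and no extended treatment-free interval. It is a share of treatment time, not a frequency of interruptions; the documents give no interruption rate.

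**The case against.** The strongest defence is that the detailed section governs. The 24-hour item sits in a summary list and is silent on cycle, whereas the re-escalation item in the same list expressly says that it applies in any cycle. The protocol sends readers to Section 7.4.2 for interruptions, including outpatient ones, which are plausibly common from cycle 3 on. The split in Section 7.4.2.1.1 also resembles the graded monitoring times in Section 7.1.1.4.1 (24 hours in cycle 2, 4 hours in cycles 3 and 4), so it could be read as the specific form of a general item.

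Part of this stands. It makes one reading plausible and makes it less certain that sites will diverge. It does not remove the conflict. A pointer is not a statement of precedence, and the schedule footnotes point the other way. The 24-hour item is itself specific to technical interruptions of more than 4 hours, and it is listed separately from the routine time for cycles 3 and 4.

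Three stronger inferences are tempting, and the documents do not support them.

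- **That the two rules cannot both be followed.** A 24-hour stay meets both. Only release at 4 hours creates a breach.
- **That the timing of cytokine release syndrome (CRS) shows what is at risk.** Section 3.2.2.4 reports 12 CRS events in the first-in-human study, all with onset within 24 hours of administration. Ten were in cycle 1 and two in cycle 2, where the texts agree. They say nothing about which time suits cycle 3 or later.
- **That the primary endpoint is compromised.** The dose-limiting toxicity window is the cycle 1 infusion period (Section 7.4.1). Adverse events are reviewed continually until the safety follow-up visit whether or not the subject is in hospital, and home-care providers must monitor and report them. A shorter stay may change how closely a subject is watched, but incomplete capture of events is not shown.

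**Conclusion.** The inconsistency is real and is confined to technical or logistical interruptions of more than 4 hours in cycle 3 or later. There the protocol lists a 24-hour minimum in two places and 4 hours of observation in a third, and no stated rule decides between them. The consequence is possible variation between sites in monitoring the same event, and a deviation for any site that acts on the shorter figure.

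The conclusion rests on two readings: that an item with no stated cycle applies to every cycle, and that observation after a re-start in hospital is the same stay to which the minimum hospitalization time refers. If the sponsor intended otherwise on either point, the text needs to say so.

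This is an internal inconsistency and not a design choice. It has no effect on dose-limiting toxicity counts, sample size or analysis. It is still worth correcting, because it concerns patient monitoring and the remedy is simple.

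**What to change.** Reconcile the synopsis, Section 7.1.1.4.1 and Section 7.4.2.1.1 to a single rule. State in each place which cycles it covers and whether the time is a hospital stay or a period of observation, and cross-reference the sections as is already done for re-start after an adverse event. Which duration should apply is for the sponsor and its clinical team to decide; this review does not propose one.

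In the same edit, check the sentence in Section 7.4.2.1.1 that refers to the assessments of cycle 1 days 1 and 2. It carries no limit by cycle, and its wording about assessments before re-start is unclear, so it should be made consistent with whatever time is chosen.

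The cost is protocol wording, with notice to sites. No change to the SAP, the data collected or the number of subjects follows from it.
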